Study Duration and Dosing	
 Each participant will participate in the study for approximately 20 weeks. This includes a screening period up to 30 days, an 84-day (12 week) treatment period, and a 28-day follow-up period after the last dose. Within 30 days of the screening visit (defined as day of consent signing), eligible participants enter a 2-part treatment phase as follows with study treatment starting on study day 1: 
 Part A: Approximately 36 participants are randomly assigned to receive either GSK2982772 60 mg three times daily (TID) or placebo TID for 42 days (6 weeks) in a 2:1 ratio. Part B: All participants who complete Part A move on to receive open label treatment of GSK2982772 60 mg TID for an additional 42 days (6 weeks). Treatment duration is a total of 84 days (12 weeks) inclusive of Parts A and B. Participants are followed-up for 28 days (4 weeks) after the last dose in Part B. Prior to amendment 01 being effective in each country, participants were randomly assigned to receive either: 
 Part A: GSK2982772 60 mg two times daily (BID) or placebo BID for 42 days (6 weeks) in a 2:1 ratio. Part B: Open label treatment for all participants who have completed Part A of GSK2982772 60 mg BID for an additional 42 days (6 weeks). 																															
Time & Events	
 Refer to Appendix 2: Schedule of Activities. During the 84-day (12 week) treatment period, participants attend the clinical for visits on Days 1, 15, 29, 43, 57, 71 and 85. At specific visits, participants must not take treatment prior to their scheduled treatment. On Days 8, 22, 36, 50, 64 and 78 participants were to be contacted by telephone and asked about their general health. Participants are given a diary card at every visit and asked to record daily study 																															

Overview of Study Design and Key Features	
	medication, concomitant medication and adverse events.

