Treatment Assignment	
 • At Screening a unique CRF number (Subject Number) is assigned. • Participants who meet screening eligibility criteria and complete pre-treatment assessments are randomised through an Interactive Response Technology System (IRTS). The IRTS confirms the participant's CRF number (Subject Number) and provides the randomisation number. • The randomisation number is generated by Clinical Statistics, prior to the start of the study, using validated internal software. Once assigned, this randomisation number must not be reassigned to any other participant in the study. • The randomisation is centrally controlled by the IRTS. • Approximately 36 participants were randomised in a 2:1 ratio to receive GSK2982772 60mg TID or Placebo TID in Part A. • Any participant that is re-screened outside of the allowed screening window at the approval of the GSK Medical Monitor, must be assigned a new unique Subject Number.

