5.5. Multiple Comparisons and Multiplicity

Overall, no adjustments will be made for multiple comparisons or multiplicity across different endpoints.

The process to reduce the false discovery rate for the transcriptomic analyses of mRNA expression is detailed in Section 10.1.3.1.

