- To identify the most robustly expressed probesets, the data can be filtered to remove low intensity probesets, low quality and control probe sets prior to analysis. This could be done simply by excluding all probesets where all observations are <6 (on the \log_2 scale). Note it has been observed empirically that when you get below 100 (6.6 on the \log_2 scale) you are into the noise of the assay. Other more stringent methods of filtering the data could be used. In total, there are 53,617 probesets that could be analysed.
- To compare the expression value for each probeset, the following linear repeated measures mixed effects model will be fitted to each probeset that passes any pre-filtering, with \log_2 (intensity) as the response variable. Randomised Treatment by visit, randomised treatment and visit will be fitted as fixed effects and participant as a random effect. Example SAS code is given below:

```
proc mixed data=data;
ods output covparms=cov lsmeans=lse estimates=Compare;
class subjid treatment visit;
model lgintensity= treatment visit treatment*visit /ddfm=kr;
repeated visit / subject=subjid type=un;
lsmeans treatment*visit / diff cl alpha=0.05;
run;
```

- For each probeset analysed adjusted means with corresponding 95% CI and fold changes with corresponding 95% CI's can be outputted. The fold change is derived from the ratio of the back-transformed estimate of the difference between adjusted means.

Transcriptomics - MicroArray RNA Analysis

- Where appropriate, particularly with microarray data, multiple testing will be considered using the Benjamini-Hochberg correction (*Benjamini, Y; J Royal Stat Soc 1995;57:289-300*) to calculate FDR adjusted p-values. Proc Multtest incorporating the FDR adjusted p-value option in SAS is used to convert the raw p-values from the proc mixed code above into the FDR adjusted p-values based on the Benjamini-Hochberg correction. Example code to generate the FDR adjusted p-values is given below:

```
data pvalues (keep = probsid label probt rename=(probt=raw_p));
    set compare;
run;

proc multtest pdata=pvalues fdr out=FDRres noprint;
run;
```

- Where the FDRes dataset will include the following columns:

p-values		
Test	Raw	False Discovery Rate
1	0.2828	0.9243
2	0.9437	0.9437
3	0.0350	0.6305
etc.		

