- Appropriate outputs will be created containing all the results for the relevant comparisons for all analysed probesets. A summary may be generated, including probeset ID, gene ID, time point, adjusted means with corresponding 95% CI for each randomised treatment group, Benjamini-Hochberg FDR adjusted p-value and fold changes corresponding 95% CI from each comparison. Note that probeset ID is required if there is more than one probeset per gene.
- For each comparison subsets of probesets will be identified based on an appropriate fold-change, for example, fold changes >1.5 or <-1.5. The proportion of probesets with fold changes >1.5 or <-1.5 will be summarised in a frequency table.
- The outputs should be reviewed by the study team and the pre-agreed subset of biologically relevant probesets will be reported within the CSR. If based on the fold-changes observed other probesets, which were not pre-specified in the RAP, are deemed relevant then these should be interpreted with caution.
- Exploratory graphical reporting on the back-transformed scale can include:
 - Log₂ (intensity) plotted against time point separately for individual participants, grouped by randomised treatment group
 - Adjusted mean intensity and 95 CI% plotted by randomised treatment group and time point.

Transcriptomics – Microarray Percentage Inhibition Analysis

- The \log_2 normalised data is back transformed and the percentage inhibition is derived on a participant level on the back transformed data for each probeset. The percentage inhibition will be determined for each probeset per participant, where it is defined as the reduction from baseline. For example:

Day X – baseline = -40% would be a 40% reduction (i.e. -40% change from baseline) which in turn is defined as a 40% inhibition. So, the percentage inhibition would be calculated as:

$$[(\text{Day } x - \text{Baseline}) / \text{Baseline}] * -100 = \% \text{ inhibition}$$

- A subset of probesets may be identified and individual participant mRNA intensities and percentage inhibitions may be listed, summarised and plotted appropriately for each selected probeset. The selected probesets will be statistically analysed appropriately, and the output from the mixed effects model summarised. The probeset, gene or gene description will be included in the outputs.

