12.10.11. Pharmacodynamic and/or Biomarker Tables

Pharmacodynamic and Biomarker: Tables					
No.	Population	IDSL / Example Shell	Title	Programming Notes	Deliverable [Priority]
Exploratory Biomarkers					
6.1.	Safety	PD_T1	Summary Statistics for Actual and Percentage Change from Baseline in Biopsy Tissue Inflammatory Biomarkers (Parts A and B)	One page for each cell type/measure by visit/time and treatment	SAC [1]
6.2.	Safety	PD_T2	Adjusted Mean (95% CI) of Percentage Change from Baseline in Biopsy Tissue Inflammatory Biomarkers (Parts A and B)	One page for each cell type/measure by visit/time and treatment/dosing regimen	SAC [1]
Pathway and Target Engagement					
6.3.	Safety	EFF_T1	Summary Statistics for Observed TEAR1 % Target Engagement (Parts A and B)	Separate summaries for sample type (Blood/Biopsy) % Target Engagement by visit/time	SAC [1]
6.4.			Summary Statistics for Predicted TEAR1 % Target Engagement based on predicted GSK2982772 trough concentrations (Parts A and B)		
6.5.	Safety	PD_T3	Adjusted Mean (95% CI) of TEAR1 % Target Engagement in Blood (Parts A and B) by Randomised Treatment		SAC [1]
6.6.	Safety	PD_T3	Adjusted Mean (95% CI) of TEAR1 % Target Engagement in Biopsy Tissue (Parts A and B) by Randomised Treatment		SAC [1]
6.7.	Safety	EFF_T1	Summary Statistics of Pathway Engagement (Parts A and B) by Randomised Treatment	Separate summaries for sample type (Blood/Biopsy)	SAC [1]
6.8.	Safety	PD_T3	Adjusted Mean (95% CI) of Pathway Engagement in Blood (Parts A and B) by Randomised Treatment		SAC [1]
6.9.	Safety	PD_T3	Adjusted Mean (95% CI) of Pathway Engagement in Biopsy Tissue (Parts A and B) by Randomised Treatment		SAC [1]

Pharmacodynamic and Biomarker: Tables					
No.	Population	IDSL / Example Shell	Title	Programming Notes	Deliverable [Priority]
mRNA Expression					
6.10.	Safety	PD_T4	Summary of mRNA Expression of Inflammatory Gene Transcripts (Parts A and B) by Randomised Treatment	Separate summaries for sample type (Blood/Biopsy) qPCR – micarray dataset	SAC2 [1]
6.11.	Safety	PD_T5	Frequency Table Summarising the Number of Probe Sets with Various Fold Change (Parts A and B) by Randomised Treatment	Separate summaries for sample type (Blood/Biopsy). Use cut-offs 1.5 and -1.5 initially. Change to -1.25 and 1.5 if no one achieves the initial cut-offs	SAC2 [1]

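### Probesets are identified, and counted in Table 6.11, on estimated fold change alone; the selection is not tied to the Benjamini-Hochberg p-values and no FDR level is fixed

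*SAP*

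**What the plan says.** Section 5.5 makes no multiplicity adjustment across endpoints but makes a commitment for transcriptomics: "The process to reduce the false discovery rate for the transcriptomic analyses of mRNA expression is detailed in Section 10.1.3.1".

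Section 10.1.3.1 then contains two strands that do not meet.

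- **Selection.** The Fold Change Analysis and MicroArray RNA Analysis blocks carry the same rule: "For each comparison subsets of probesets will be identified based on an appropriate fold-change, for example, fold changes >1.5 or <-1.5". The proportion of probesets beyond the cut goes into a frequency table. On the number of candidates: "In total, there are 53,617 probesets that could be analysed". Filtering of low-intensity, low-quality and control probesets beforehand is allowed but not required.
- **False discovery.** Multiple testing is to be considered by the BH method where appropriate, with example code. The adjusted p-values are listed in a summary that is itself optional. No FDR level is given.

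For the CSR, reporting is limited to a subset agreed in advance, followed by: "If based on the fold-changes observed other probesets, which were not pre-specified in the RAP, are deemed relevant then these should be interpreted with caution".

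In Section 12.10.11, Table 6.11 counts probesets by fold change, separately for blood and biopsy, with the notes "Use cut-offs 1.5 and -1.5 initially" and "Change to -1.25 and 1.5 if no one achieves the initial cut-offs". Tables 6.13 to 6.15, all titled for blood, are to be produced only for probesets significant on adjusted p-values. Tables 6.10 to 6.12, which cover both tissues, carry no such condition.

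**The concern.** An estimated fold change is a point estimate. With about 12 participants in the smaller arm and tens of thousands of probesets, some estimates may pass a fixed cut by chance alone. A rule that ignores the standard error cannot separate these from real effects. It also favours noisy probesets, because the chance of passing a fixed cut under the null rises with the probeset's SD.

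The BH calculation could guard against this, but the plan does not connect it to the step that selects probesets. Three consequences follow:

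- Table 6.11 can show a non-zero proportion beyond 1.5-fold when the drug does nothing, and it gives the reader no benchmark.
- A probeset outside the pre-agreed subset can be raised on the same uncontrolled quantity, with only a request for caution.
- For biopsy tissue, no listed table applies an adjusted p-value condition at all.

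**Working it through.** The SAP states no false-positive rate, FDR level or power for this rule, so there is no planned figure to reproduce. The check asks how many probesets would pass if the drug had no effect.

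**Inputs**

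- Probesets: 53,617 (Section 10.1.3.1), the maximum before optional filtering.
- Participants: "Approximately 36 participants were randomised in a 2:1 ratio to receive GSK2982772 60mg TID or Placebo TID in Part A" (Section 2.3), so 36 × 2/3 = 24 active and 36 × 1/3 = 12 placebo.
- Cut: 1.5-fold in either direction, i.e. an absolute difference in mean log2 intensity above log2(1.5) = 0.585. This takes a fold change below -1.5 to mean a ratio below 1/1.5.
- Between-participant SD of log2 intensity at a visit: not in the SAP, so assumed and varied.
- Probesets treated as independent, estimates as normal; one visit and one tissue.

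**Formulas**

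The model has treatment, visit and their interaction, with no baseline covariate. With complete data the contrast at a visit is a difference in means:

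- SE = SD × √(1/24 + 1/12) = 0.354 × SD
- p = 2 × [1 − Φ(0.585 / SE)]
- Expected number = 53,617 × p
- Chance of at least one = 1 − (1 − p)^53,617

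**Results**

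| Assumed common SD | SE | p | Expected number | Chance of at least one |
|---|---|---|---|---|
| 0.30 | 0.106 | 3.49 × 10⁻⁸ | 0.002 | 0.2% |
| 0.35 | 0.124 | 2.28 × 10⁻⁶ | 0.12 | 11% |
| 0.40 | 0.141 | 3.53 × 10⁻⁵ | 1.9 | 85% |
| 0.50 | 0.177 | 9.36 × 10⁻⁴ | 50 | about 100% |
| 0.70 | 0.247 | 0.0181 | 970 | about 100% |

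The chance of at least one reaches 95% at a common SD of 0.41 and 99% at 0.42.

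**Unequal SDs.** Probesets will not share one SD, and the noisy ones drive the count. If only 10% had SD 0.5 and the rest contributed nothing, the expected number is 5,362 × 0.000936 = 5.0 and the chance of any is 1 − exp(−5.0) = 99%. With lognormal SDs (median 0.25, log-SD 0.4), about 20 are expected and the chance is about 100%. With median 0.20 and log-SD 0.3, it is 31%.

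**Fewer probesets or samples.** If 20,000 probesets survived filtering (an assumed number), SD 0.40 gives 0.71 expected and 51%, and SD 0.45 gives 4.7 and 99%. With 20 v 10 evaluable participants, the common SD needed for 95% falls to 0.37.

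**Adding a BH condition.** In 400 simulated null data sets (t-tests on 34 df), requiring BH-adjusted p ≤ 0.05 as well as the fold-change cut reduced the chance of identifying any probeset from 100% to 3.5% at common SD 0.5. In the lognormal case with median 0.25 and log-SD 0.4 it fell from 100% to 0.5%. The 0.05 is assumed, since the SAP gives no level.

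**The case against.** A reader of the selection sentence alone might infer that the transcriptomic plan has no false-discovery control. The SAP does not support that. Section 10.1.3.1 provides BH-adjusted p-values, and Tables 6.13 to 6.15 are restricted by them. CSR reporting is limited to a pre-agreed subset, with caution asked for anything beyond it. What remains is narrower: the selection rule, Table 6.11 and the biopsy displays sit outside the restriction, and no level defines significance.

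A reader might also infer that false identifications are almost certain whatever the data look like. That does not follow either. The SAP gives no SD, and the chance is 0.2% at a common SD of 0.30. The figure of 53,617 is a ceiling, and filtering aimed at assay noise could remove the most variable probesets and cut the counts more than in proportion. Independence is an assumption too.

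Further, Table 6.11 is by its title a frequency table and claims no drug effect, the endpoint is exploratory and analysed after the main reporting, and the 1.5 cut is offered only as an example. Screening on fold change with adjusted p-values shown separately is an accepted exploratory layout. This stands as a reason to rate the point minor. It does not remove it, because the SAP itself promises FDR handling here and then leaves it out of the step that identifies probesets, and the summary that would show both quantities together is optional.

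Finally, BH at 5% does not bound false identifications at 5% of null studies. The bound is per comparison. With two tissues and two post-baseline visits handled as four independent families, the chance of any is up to 1 − 0.95⁴ = 18.5%.

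**Conclusion.** The point holds as a minor one. Identification of probesets and the counts in Table 6.11 rest on estimated fold change alone. No FDR level is fixed, and the adjusted p-value restriction reaches only the blood Tables 6.13 to 6.15.

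With no drug effect, a non-empty list is likely under moderate variability and near certain at a common SD of about 0.42 or more, or if a modest share of probesets is noisier than that. At a common SD of 0.30 or below, the 1.5-fold rule would almost never produce one. These figures rest on 24 v 12 complete participants, normal estimates, independent probesets, no filtering and an SD the SAP does not supply. The favouring of noisy probesets does not depend on the exact SD.

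**What to change.** 1. State an FDR level in Section 10.1.3.1, for example 0.05 applied per comparison, and make the BH calculation firm rather than something to be considered.
2. In both the Fold Change Analysis and MicroArray RNA Analysis blocks, identify a probeset only if it meets that level and the fold-change cut, in blood and in biopsy.
3. Extend the adjusted p-value restriction of Tables 6.13 to 6.15 to the biopsy tables.
4. In Table 6.11, show the number meeting the fold-change cut beside the number also meeting the FDR level, and label the first count descriptive.
5. Apply the same double condition to any probeset outside the pre-agreed subset that is taken into the CSR.
6. Treat only the Day 43 contrast as GSK2982772 versus placebo. By Day 85 all Part A completers have moved to open-label active drug (Section 2.3), so the contrast there is between randomised sequences.

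The cost is a few sentences and one extra column, using p-values for which Section 10.1.3.1 already gives example code. The downside is that fewer probesets will be listed, and with about 36 participants some real effects will miss the FDR level; the descriptive count keeps them visible.

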12. APPENDICES

12.1. Appendix 1: Protocol Deviation Management and Definitions for Per Protocol Population

12.1.1. Exclusions from Per Protocol Population

A participant meeting any of the following criteria will be excluded from the Per Protocol population:

Number	Exclusion Description
01	Inclusion #9 – Informed Consent: Informed Consent not available at site or Patient did not sign or date
02	Inclusion #2 – Eligibility: Other medical conditions
03	Inclusion #3 – Eligibility: Confirmed diagnosis of UC
04	Inclusion #4 – Eligibility: Total Mayo score and endoscopy subscore
05	Inclusion #5 – Eligibility: Stable concurrent medication
06	Inclusion #6 – Eligibility: Prior treatment
07	Incorrect randomisation or study unblinding procedures

A participant meeting any of the following criteria will be reviewed for exclusion from the Per Protocol population:

Number	Exclusion Description
08	Exclusion #17 – Concomitant Medication

12.2. Appendix 2: Schedule of Activities

12.2.1. Protocol Defined Schedule of Events

Procedures	Screening (-30)	Screening (-7 to -30)	Treatment Period ¹⁸													Early Withdrawal ¹⁹	Follow Up (±3) ²⁰
			PART A							PART B							
			Day 1	Day 8 (±3)	Day 15 (±3)	Day 22 (±3)	Day 29 (±3)	Day 36 (±3)	Day 43 (±3) (week 6)	Day 50 (±3)	Day 57 (±3)	Day 64 (±3)	Day 71 (±3)	Day 78 (±3)	Day 85 (+2) (week 12)		
Site Visit	X	X	X		X		X		X		X		X		X	X	X
Phone call				X		X		X		X		X		X			
General/Safety Assessments and Procedures																	
Informed Consent	X																
Subject Demography	X																
Full medical history ¹	X																
Inclusion/Exclusion Criteria	X																
Full physical exam ²	X													X	X	X	
Brief physical exam			X ⁴		X		X		X ⁴		X		X				
Vital signs (BP, HR, RR, temperature)	X		X ⁴		X		X		X ⁴		X		X		X	X	X
12-lead ECG ³	X		X ⁴		X		X		X ⁴		X		X		X	X	X
Concomitant medication review & AE reporting/SAEs ⁵			X-----														
PROs/Questionnaires/Disease Assessments and Procedures																	
Columbia Suicide Severity Rating	X		X ⁴						X ⁴						X	X	

Procedures	Screening (-30)	Screening (-7 to -30)	Treatment Period ¹⁸													Early Withdrawal ¹⁹	Follow Up (±3) ²⁰
			PART A						PART B								
			Day 1	Day 8 (±3)	Day 15 (±3)	Day 22 (±3)	Day 29 (±3)	Day 36 (±3)	Day 43 (±3) (week 6)	Day 50 (±3)	Day 57 (±3)	Day 64 (±3)	Day 71 (±3)	Day 78 (±3)	Day 85 (+2) (week 12)		
Scale (C-SSRS)																	
IBDQ ⁶			X ⁴							X ⁴						X	X
UCEIS, Modified Riley, Geboes Index	X-----X ⁷									X ⁴						X	X
Mayo Score (including sigmoidoscopy and biopsy)	X-----X ⁷									X ^{4, 8}						X	X ⁹
Partial Mayo Score	X-----X ⁷				X		X			X ⁴						X	X
Study Treatment																	
Randomisation			X														
Study medication (three times daily) ¹⁰			X-----XX-----X ¹¹														
Dispensing of study medication			X		X					X							
Dispensing of diary cards			X		X		X			X		X		X			
Collection of diary cards					X		X			X		X		X		X	
Laboratory (Safety) Assessments and Procedures																	
TB, HIV, Hep B, Hep C Ab, C. Difficile toxin	X																
FSH & estradiol (if applicable)	X																
Serum pregnancy test (WCBP only)	X																

Procedures	Screening (-30)	Screening (-7 to -30)	Treatment Period ¹⁸												Early Withdrawal ¹⁹	Follow Up (±3) ²⁰	
			PART A						PART B								
			Day 1	Day 8 (±3)	Day 15 (±3)	Day 22 (±3)	Day 29 (±3)	Day 36 (±3)	Day 43 (±3) (week 6)	Day 50 (±3)	Day 57 (±3)	Day 64 (±3)	Day 71 (±3)	Day 78 (±3)			Day 85 (+2) (week 12)
Urine pregnancy test (WCBP only) ¹²			X ⁴		X		X		X ⁴		X		X		X	X	X
Haematology, chemistry, urinalysis	X		X ⁴		X		X ¹³		X ⁴		X ¹³		X ¹³		X	X	X
Faecal calprotectin ¹⁴		X	X		X		X		X		X		X		X	X	
Blood sample for exploratory biomarkers and TE ¹⁵			X ⁴						X ⁴						X	X	
PK blood samples GSK2982772 ¹⁶			X						X ⁴						X	X	
Biopsies for PK, inflammatory biomarkers, mRNA, TE & pathway marker analysis		X-----X ⁷							X ⁴						X	X ⁸	
Pharmacogenetic sample (PGx) ¹⁷			X														

Footnotes:

1. Full medical history (includes past and current conditions, medication history, substance usage, and family history of premature CV disease).
2. Full physical exam (includes height/weight at screening, height not measured at later time points).
3. Triplicate ECG to be performed at screening only and if stopping criteria are met.
4. Pre-dose.
5. Any SAEs assessed as related to study participation (e.g., protocol-mandated procedures, invasive tests, or change in existing therapy) or related to a GSK product will be recorded from the time a participant consents to participate in the study up to and including any follow-up. AEs will be collected from the start of Study Treatment until the follow-up contact.
6. PRO assessments should be conducted before any tests, procedures or assessments to avoid influencing the participants' perception.

7. Sigmoidoscopy may be performed at any time during the screening window as an additional visit (if required) up to Day -7 in order for central reading confirmation of Mayo Score for inclusion. If a shorter window is required (e.g., within Day -3 to Day -7), this will be permitted as long as it has been confirmed with the sponsor and central reader that results of the Mayo endoscopy score will be available before end of screening window. Histological disease (e.g., UCEIS, MRS and Geboes Index) along with Mayo score assessments will also be completed.
8. Sigmoidoscopy may be performed on a separate day within the Day 43 visit window allowance (± 3 days). A separate visit to perform sigmoidoscopy is only allowed to accommodate scheduling. This separate visit should be done before the full Day 43 visit where PK, clinical laboratory tests and all other required Day 43 procedures are performed. Participants must not take their study medication at home in the morning before the sigmoidoscopy procedure and also the morning before the full Day 43 visit, if being done on a separate day. Dispensing of study medication must be done at the 2nd visit (if separate visits are performed).
9. Biopsy only required at Early Withdrawal visit if after at least 14 days of treatment and prior to Day 43 or if after Day 57 and prior to Day 85.
10. Participants must take study medication three times a day approximately 8 hours apart. Exact time of dosing to be recorded in diary cards. On Day 43 and 85, participants must not take their study medication at home in the morning. Participant will complete specified pre-dose assessments and then will be administered their morning dose of medication at site on Day 43. On Day 85, participants are no longer receiving study medication.
11. In Part A, participants will be randomised 2:1 to GSK2982772 60 mg or placebo three times daily for 42 days. At the Day 43 visit, all participants who have completed Part A, will move in to Part B open label treatment with GSK2982772 60 mg three times daily for 42 days.
12. If urine pregnancy test is positive, a confirmatory serum pregnancy test must be performed.
13. Urinalysis not required on Days 29, 57 and 71.
14. Participants can provide a faecal sample at any time during the screening window and up to 48 hours prior to any visit where FCP is being collected. Please see laboratory manual for full details on sample handling and procedure.
15. Blood samples for exploratory biomarkers and Target engagement. See laboratory manual for full details on sample collection, handling and shipment.
16. PK blood samples for GSK2982772 will be taken pre-dose on Day 43. Post-dose serial PK samples will be taken on Days 1 and Day 43 at the following time points: 1, 2, 4, and 6 hours and trough on Day 85 or Early Withdrawal.
17. A PGx blood sample is collected at the baseline visit (Day 1), after the participant has been randomized and provided informed consent for genetic research. If the sample is not collected at the baseline visit, it can be collected at any time during the study after randomization.
18. Visit windows during the treatment period are relative to Day 1.
19. If a participant withdraws from the study, every effort will be made for the participant to complete an Early Withdrawal visit prior to the Follow Up visit.
20. Follow-up visit should be completed 28 days (± 3 days) after the last dose of study medication.

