
 To investigate the preliminary efficacy of 60 mg three times daily doses of GSK2982772 in achieving symptomatic clinical remission after 6 and 12 weeks of treatment in subjects with active ulcerative colitis. 	
 Change from baseline in partial Mayo score.

 To investigate the plasma concentrations of GSK2982772 following 60 mg three times daily in subjects with active ulcerative colitis. 	
 Pre-dose plasma concentrations of GSK2982772 at Day 43 (Week 6). Post-dose plasma concentrations of GSK2982772 on Days 1 and 43 (Week 6) at 1, 2, 4 and 6 hours. Trough concentrations on Day 85 (Week 12).
Exploratory Objectives	Exploratory Endpoints

 To investigate the effect of 60 mg three times daily doses of GSK2982772 on expression of inflammatory biomarkers in mucosal tissue biopsies in subjects with active ulcerative colitis. 	
 Change from baseline in inflammatory markers which may include, but are not limited to IL-1, IL-6, IL-8, MMP3, TNFα, IFNγ.

 To investigate pathway and target engagement following 60 mg three times daily doses of GSK2982772 in blood and colon biopsy tissue. 	
 Pharmacology biomarker endpoints may include, but are not limited to the following, pre-dose at Days 1, 43 (Week 6) and trough on Day 85 (Week 12), as applicable and if evaluable samples and data permit: 
 Target Engagement Assay RiP1 (TEAR1) in blood and colon tissue. Phosphorylated or total RIP1, MLKL, RIP3, cleaved and total caspase 3 and 8 signatures in colon biopsy tissue.

 To investigate the concentration of GSK2982772 and possible drug-related material, as well as specific distribution within tissue if feasible, in the colon tissue 	
 Pre-dose GSK2982772 and possible drug-related material concentrations, as well as specific distribution within tissue if feasible, in colon biopsies at Days 43 (Week 6) and 85 (Week 12), as evaluable samples

Objectives	Endpoints
after 60 mg three times daily doses of GSK2982772.	and data permit.

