12.3. Appendix 3: Assessment Windows

12.3.1. Definitions of Assessment Windows for Analyses

No Assessment Windows will be defined for Analysis, and summaries and analyses will be based on nominal visits.

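### Week 12 samples are called trough and analysed by nominal visit, but the visit may fall up to two days after the apparent end of dosing, which can bias the Day 85 plasma trough downward

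*SAP*

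**What the plan says.** **End of dosing.** SAP 2.3 has eligible participants enter the two-part treatment phase "with study treatment starting on study day 1", and adds "Treatment duration is a total of 84 days (12 weeks) inclusive of Parts A and B". Footnote 10 in 12.2.1 says "On Day 85, participants are no longer receiving study medication". The design overview in 2.3 puts follow-up at Day 112, and footnote 20 sets follow-up 28 days after the last dose.

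**Visit timing.** The schedule column reads "Day 85 (+2) (week 12", so the visit may be on Day 85, 86 or 87. Footnote 18 ties the window to the first day and not to the last dose: "Visit windows during the treatment period are relative to Day 1".

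**Labels.** The secondary plasma endpoint in 2.2 is "Trough concentrations on Day 85 (Week 12". The same section calls the Week 12 target-engagement sample a trough and the Week 12 biopsy concentration pre-dose.

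**Analysis time.** Section 12.3.1 defines no analysis windows: "summaries and analyses will be based on nominal visits". Section 12.5.2 uses scheduled time in summaries, figures, models and derived parameters, and shows actual time only in listings.

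**Day 43.** Table 1 in 2.1 and section 9.1.1.1 replace the observed Day 43 pre-dose value by a predicted trough for PK/PD work, because the half-life is 2 to 3 h and a clinic sample may come some hours after the usual dose time. Nothing comparable is given for Day 85.

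**The concern.** A visit on Day 86 or 87 is inside the window, so it is not a deviation, and its sample enters the Day 85 summaries as a trough. If the last dose was on Day 84, that sample was drawn more than a day after it. The SAP treats a delay of about 3 h on Day 43 as needing correction. It sets no correction, time limit or exclusion for Day 85, where the window allows a further 24 to 48 h.

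At stake is the Day 85 plasma summary required by 9.1.1.1 and the plots of pre-dose concentration against day (Figures 4.4 and 4.5). A drop from Day 43 to Day 85 could be read as lost exposure when it comes only from visit timing. Figure 4.6, which sets plasma against tissue concentration, uses the same samples. Target engagement at Week 12 (Tables 6.3, 6.5 and 6.6) comes from the same visit.

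**Working it through.** **Inputs from the SAP.** Half-life 2 to 3 h, with 2.5 h used in the Day 43 equation, and a usual dose time of 07:00 (9.1.1.1). Doses about 8 h apart (12.2.1, footnote 10). Window Day 85 to 87 (12.2.1).

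**Assumptions.** Doses at 07:00, 15:00 and 23:00. Last dose at 23:00 on Day 84, so the true trough is at 07:00 on Day 85. Clinic sample between 07:00 and 10:00. First-order elimination.

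**Formula.** Fraction of trough left = 0.5^(h / t½), where h is hours past trough. Half-lives past trough = h / t½.

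**The SAP's own example.** A sample 3 h late with a 3 h half-life: 0.5^(3/3) = 0.50. This matches the one-half in 9.1.1.1.

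**Results (half-lives past trough, with % of trough left).**

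| Sample | h | t½ = 2 h | t½ = 2.5 h | t½ = 3 h |
|---|---|---|---|---|
| Day 85, 07:00 | 0 | 0 (100%) | 0 (100%) | 0 (100%) |
| Day 85, 10:00 | 3 | 1.5 (35%) | 1.2 (44%) | 1.0 (50%) |
| Day 86, 07:00 | 24 | 12 (0.02%) | 9.6 (0.13%) | 8 (0.39%) |
| Day 86, 10:00 | 27 | 13.5 (0.009%) | 10.8 (0.056%) | 9 (0.20%) |
| Day 87, 07:00 | 48 | 24 (<0.002%) | 19.2 (<0.002%) | 16 (<0.002%) |

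**Effect on the mean.** If a share f of visits is late and a late sample holds a fraction r of trough, the mean is (1 − f) + f·r of its true value, so it is understated by f·(1 − r). With r at most 0.0039, that is about f. The SAP does not state f. For assumed shares of 10%, 20% and 40%, the mean is about 10%, 20% and 40% too low. This takes late and on-time participants to have the same true trough.

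**Back-extrapolation does not rescue a late sample.** At 27 h past trough the multiplier is 2^(27/3) = 512, 2^(27/2.5) ≈ 1,780 or 2^(27/2) ≈ 11,600. That is a 23-fold spread across the SAP's own half-life range.

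**Which day is the last dosing day?**
- 84 days from Day 1 ends on Day 84, and 112 − 28 = 84 agrees.
- Footnote 11 gives Part B 42 days from the Day 43 visit, which may move by 3 days. Counted from the visit, the last dosing day is visit day + 41: Day 81 for a visit on Day 40, Day 87 for a visit on Day 46.
- After a Day 81 stop, even an on-time 07:00 sample on Day 85 is 72 h past trough (72 / 2.5 = 28.8 half-lives). A Day 87 stop contradicts footnote 10.

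**The case against.** **Dosing may run up to the visit.** No sentence says that the last dose is on Day 84. Footnote 10 also says "On Day 43 and 85, participants must not take their study medication at home in the morning". For Day 43 this plainly means the visit, wherever it falls in its window. Read the same way for Day 85, it suggests that dosing continues to the eve of the visit, and the sample would then be near trough. This stands as an ambiguity. A reader might infer that late Week 12 samples are established washout samples, but the documents support that only if dosing ends on Day 84. The 84-day statement, the Day 112 follow-up and the last sentence of footnote 10 point that way, and the home-dose instruction points the other.

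**Tissue and target engagement.** A reader might infer that these also fall towards zero. The SAP uses its 2 to 3 h half-life only to correct a plasma sample. It gives no tissue half-life and no rate at which engagement is lost. The mistiming is shared, but the size of its effect is unknown.

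**Nine or more half-lives.** That figure is tempting but not general: a 07:00 sample on Day 86 with a 3 h half-life is at 8.

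**Existing safeguards and limited use.** Section 12.5.2 has major timing deviations assessed and shows actual times in listings. An in-window visit is not a deviation, though, and listings do not change the summaries. Concentrations are only described, with no formal analysis, and PK/PD work uses the Day 43 predicted trough. Both points limit the consequence without removing it for the Day 85 summary and Figures 4.4 and 4.5.

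**Conclusion.** The point holds for plasma, conditionally. If dosing stops on Day 84, a sample from a Day 86 visit carries about 0.4% or less of the trough (8 to 13.5 half-lives past it, for sampling at 07:00 to 10:00). A Day 87 sample carries practically none (16 or more half-lives). Analysed by nominal visit, these pull the mean Day 85 trough and Figures 4.4 and 4.5 down by roughly the share of late visits, which is unknown. Visits on Day 85 itself are near trough under the same assumption, at 35% to 100% for 07:00 to 10:00.

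For tissue concentration and target engagement, only the mistiming is established. Separately, the 84-day statement in 2.3 and footnotes 10, 11 and 18 in 12.2.1 leave the last dosing day unclear and must be reconciled. The result rests on the SAP's half-life range, the assumed 8-hourly clock times and first-order decay.

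**What to change.** 1. Reconcile the 84-day statement in 2.3 with footnotes 10, 11 and 18 in 12.2.1, so that the last dosing day is unambiguous relative to the Week 12 visit.
2. In 9.1.1.1, derive actual hours from the last recorded dose to each Day 85 sample. Footnote 10 already has exact dose times entered in the diary cards. This works under every reading of the schedule.
3. Summarise a Day 85 plasma sample as trough only if it falls within one 8 h dosing interval plus a short tolerance stated in advance, in line with the delay that the SAP already treats as correctable on Day 43 (3 h in its example). List later samples and leave them out of the Day 85 trough summary and Figures 4.4 to 4.6. A loose limit would not serve: 16 h after the last dose is 8 h past trough and still admits samples at 6%, 11% or 16% of it (half-life 2, 2.5 or 3 h).
4. For tissue concentration and target engagement, keep all samples in the main tables, show time since last dose, and add a sensitivity summary without samples taken a day or more after the last dose. The pathway-engagement tables (6.7 to 6.9) need no exclusion.
5. Align the programming note for Table 4.1, which leaves out Day 85, with 9.1.1.1, which includes it.

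The cost is SAP wording, one derived variable and one extra summary. The downside is that a few Day 85 plasma samples leave the trough summary.
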